4.3. Analyses

4.3.1. Descriptive Analysis

This DUS is descriptive in nature; and frequency and rates of virologic failure, baseline resistance, and treatment emergent resistance will be reported separately for the RPV and EFV-treated groups.

4.3.2. Specific Comparisons

Specific comparisons will be made with respect to patient clinical characteristics, rates of virologic failure, baseline resistance, and treatment emergent resistance between the RPV and EFV-containing regimen treatment groups.

4.3.3. Nested Case-Control

A nested case-control analysis will be performed to estimate the odds of virologic failure associated with ARV treatment adherence and separately with adherence to pill intake with food by comparing the exposure level (>80% vs. \leq 80%) of each case with that of individually matched controls. The odds ratio of virologic failure and 95% CI will be reported for nonadherent patients compared with adherent patients with respect to daily medication adherence and adherence to dietary instructions, separately.

4.4. Missing Data Handling

An evaluation of missing data will be conducted to assess the assumptions under which inference is valid. Missing data will be categorized into: missing completely at random (MCAR) in which there is no difference in subjects with missing data and those with complete data; missing at random (MAR) in which missing data are based on known or observed values of the collected variables, but not unmeasured data; and missing not at random (MNAR) where missing data is dependent on variables not measured. The evaluation will consist of comparing the distribution of the observed variables for patients with complete data with the distribution of observed variables for patients with missing data. Strategies for managing missing data may include limiting the analysis to patients with complete data or missing data imputation to estimate the value of the missing data.

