4. STATISTICAL METHODS

4.1. Sample Size and Study Precision

4.1.1. DUS Sample Size and Study Precision

The sample size targets will produce an error rate of no more than 5%. A minimum of 600 patients exposed to RPV-containing regimens will be included in the DUS to assess the proportion of appropriate use of RPV formulations. The error rate under these assumptions and an observed proportion of appropriate use of 95% is estimated at \pm -0.02.

Proportion		
of	95% CI	95% CI
appropriate	error (+/-)	error (+/-)
use (%)	with 400	with 600
	patients	patients
70	0.04	0.04
75	0.04	0.03
80	0.04	0.03
85	0.03	0.03
90	0.03	0.02
95	0.02	0.02

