Allocation of treatment is not subject to randomization. Patients will likely be channeled to treatment based on several measured and unmeasured characteristics and based on treatment guidelines. For example, treatment guidelines for the FDC of EFV are likely to channel ARV-treatment experienced patients into the FDC as opposed to the single agent formulation of EFV. This potentially introduces associations between exposures and outcomes that are confounded and may result in imbalances in the exposure groups when comparing EFV-containing regimens and RPV-containing regimens.

All comparative analyses will be conducted under the assumption that unmeasured or missing effect modifiers, risk factors, or confounders are distributed equally across the RPV and EFV treatment groups and that the effects of these unmeasured or missing variables are non-differential with respect to treatment.

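### Section 4.4 sorts missing data into MCAR, MAR or MNAR from observed variables alone, which can argue against MCAR but cannot confirm it or separate MAR from MNAR

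*Protocol*

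**What the plan says.** Protocol section 4.4 (Missing Data Handling) opens with its purpose: "An evaluation of missing data will be conducted to assess the assumptions under which inference is valid". It then commits to placing missing data in one of three categories:

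- MCAR: "in which there is no difference in subjects with missing data and those with complete data".
- MAR: "missing data are based on known or observed values of the collected variables, but not unmeasured data".
- MNAR: "missing not at random (MNAR) where missing data is dependent on variables not measured".

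The evaluation is fixed as "comparing the distribution of the observed variables for patients with complete data with the distribution of observed variables for patients with missing data". No other step, test, threshold or decision rule is given. The section closes with "Strategies for managing missing data may include limiting the analysis to patients with complete data or missing data imputation". Neither option is tied to any of the three categories.

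Section 5 (Study Limitations) adds that comparative analyses will assume that "unmeasured or missing effect modifiers, risk factors, or confounders are distributed equally across the RPV and EFV treatment groups".

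**The concern.** The classification needs information that the evaluation does not use. Whether missingness depends on unseen values is the question that separates MNAR from MAR, and a comparison of seen values cannot answer it. Because MCAR is worded as the absence of a difference, a null comparison would naturally be read as MCAR, and a non-null one as MAR. No result leads to MNAR.

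The outcomes at stake are primary objectives (section 1.3.1). Under section 4.2.2, a patient starting above 500 copies/ml can be classified as failing only with a viral load after six months, and a patient undetectable at baseline only with two consecutive values. Treatment-emergent resistance needs a resistance test during therapy. In routine care, patients who are failing or disengaging may well be the ones without these results. Section 5 itself concedes that data may be lacking through loss to follow-up or because fields are not routinely collected. A report could then state that the missing-data assumption had been checked when it had not.

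**Working it through.** **1. What the comparison can return, against what each category requires**

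| Comparison of observed variables | Natural reading under section 4.4 | Mechanisms compatible with the result |
|---|---|---|
| No difference found | MCAR | MCAR; MNAR driven by the unseen value alone; MAR too weak to detect |
| Difference found | MAR | MAR; MNAR that also relates to observed variables |

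MNAR is compatible with both rows and identified by neither. This follows from the section's own definitions and needs no numbers.

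**2. How often would MNAR data look like MCAR?** The protocol gives no missing fraction, test or threshold, so all inputs but one are assumptions. The exception is the sample size of 600, from section 4.1.1: "A minimum of 600 patients exposed to RPV-containing regimens will be included in the DUS". Assumed: event prevalence 15%; outcome missing in 30% or 40% of patients with the event and 10% of those without; 1 or 8 observed covariates compared by t-test; MCAR declared if no p<0.05, with or without Bonferroni correction; 1,500 simulated datasets per setting. All datasets are truly MNAR. Share that would be labelled MCAR:

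| Missingness depends on | 1 covariate | 8 covariates, uncorrected | 8 covariates, Bonferroni |
|---|---|---|---|
| Unseen outcome only; covariates unrelated to outcome | 95% | 66–67% | about 95% |
| Unseen outcome only; correlation 0.6 with covariates | 18–47% | 23–39% | 69–81% |
| Unseen outcome plus one covariate (log-OR 0.4 per SD); correlation 0 to 0.6 | 0–11% | about 1–8% | 7–35% |

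The share runs from about 0% to 95%. In the remaining datasets a difference is found and the data would be read as MAR, which is also wrong.

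**3. Bias in a single-group proportion.** Assumed: true failure p = 12%; viral load missing in m0 = 15% of non-failures and in a fraction m1 of failures.

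Complete-case proportion = p(1−m1) / [p(1−m1) + (1−p)(1−m0)]

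- m1 = 15%: 0.102 / (0.102 + 0.748) = 12.0%, no bias.
- m1 = 30%: 0.084 / (0.084 + 0.748) = 10.1%.
- m1 = 45%: 0.066 / (0.066 + 0.748) = 8.1%.

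Imputation under MAR would not repair this if the observed covariates are unrelated to failure: it fills the gaps at about the observed rate, so the 10.1% stays near 10.1%. With m1 = 30%, the true failure proportion among patients with missing viral load is 0.036 / (0.036 + 0.132) = 21.4%.

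**4. Departure a sensitivity analysis must cover.** The odds ratio of failure, missing against observed patients, is [m1/(1−m1)] / [m0/(1−m0)]:

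- m1 = 30%: (0.30/0.70) / (0.15/0.85) = 2.4.
- m1 = 45%: (0.45/0.55) / (0.15/0.85) = 4.6.

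**5. Bias in the ratio between groups**

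- Same mechanism in both groups (missing in 30% of failures, 10% of non-failures), true 15% and 10%, risk ratio 1.50. Complete cases: 0.105 / (0.105 + 0.765) = 12.07% and 0.070 / (0.070 + 0.810) = 7.95%; ratio 1.52. The odds ratio is unchanged, since both odds are multiplied by 0.70/0.90.
- Different mechanisms, true 12% in both groups, true ratio 1.00. If one group has 30% and 15% missing as in step 3, and the other has missingness unrelated to failure, the ratio is 10.1 / 12 = 0.84.

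**The case against.** The strongest reply is that this is a narrow wording error with no demonstrated effect on a planned estimate. Several parts of that reply stand.

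- A reader might infer that the comparison will usually label MNAR data as MCAR. The protocol does not support this. It states no test, threshold or multiplicity rule, and the share moves from about 0% to 95% with inputs it does not give. Missingness related to observed variables is plausible, given the covariates listed in section 4.2.4, and would mostly produce a MAR label.
- A reader might infer that an MCAR label clears a complete-case analysis. The text ties no label to a method; its two strategies are offered permissively, and imputation is equally open.
- A reader might infer that the rilpivirine–efavirenz ratio must be biased. Step 5 shows it is almost unaffected under a common mechanism.
- The illustration in step 3 resembles the 12-month proportions of section 4.5.3. It does not carry over directly to the incidence rates and Poisson models, which use person-time, or to the proportions treated in accordance with the SmPC, whose denominator is all initiators.
- Imputation models and sensitivity analyses are commonly left to a statistical analysis plan, and one may exist. Their absence here is not a fault in itself. Section 5 states its assumption of balance openly.

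What does not stand is the suggestion that the matter can wait for that plan. The protocol fixes both the classification and the means of making it, so a plan that followed section 4.4 would inherit a step that cannot work. The section 5 assumption does not repair this: it assumes balance between groups and tests nothing.

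**Conclusion.** The point holds in this form: section 4.4 promises a three-way classification of missingness and a judgement on the validity of inference that its only stated evaluation cannot deliver. Evidence against MCAR is obtainable; confirmation of MCAR, or separation of MAR from MNAR, is not. The error is certain because it rests on the section's own definitions.

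The consequence is possible false reassurance, equally for complete-case analysis and for MAR imputation. Its size is not knowable from the protocol. Under the assumed inputs, a 12-month failure proportion of 12% would read as 10.1%, or 8.1% with heavier missingness among failures. A material effect on the between-group ratio mainly requires a mechanism that differs by treatment; in the example a true 1.00 becomes 0.84. The correction should be made because it is cheap and protects primary outcomes. It does not show that the planned comparison is invalid.

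**What to change.** In section 4.4:

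1. Delete the assignment of missing data to MCAR, MAR or MNAR.
2. Keep the comparison of patients with complete and incomplete data, but only to describe missingness and to choose variables for imputation or adjustment.
3. State that MNAR cannot be tested from the observed data, and that finding no difference does not justify a complete-case analysis.
4. Add an MNAR sensitivity analysis for virologic failure and treatment-emergent resistance, for example delta-adjusted imputation or a tipping-point analysis. Vary the departure separately for rilpivirine and efavirenz, over a range wide enough to include odds ratios of about 5 between missing and observed patients; a range stopping at 3 would not reach the 4.6 in step 4. Report whether the conclusions change.

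The choice of main method, including whether it is multiple imputation, can be left to the statistical analysis plan. The cost is a short rewording plus a few extra analysis runs and tables on data already held.

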4.5. Statistical Analysis Plan

4.5.1. Analysis of Baseline Characteristics

Baseline characteristics including demographics, medical history and use of medications at cohort entry will be described separately for the RPV and EFV-treated groups. The analysis will report the frequency distribution (number and percentage of patients) for categorical variables and descriptive statistics (median, mean, standard deviation [SD]) for continuous variables. Descriptive statistics will be used to evaluate and compare the baseline characteristics of the treatment groups and analyze the prescribing patterns of RPV-containing regimens and EFV-containing regimens. Characteristics to be analyzed will be covariates and all potential confounding factors listed in Section 4.2.3.

4.5.2. Analysis of Appropriate Use

This analysis will describe and summarize the prescribing of RPV and EFV-containing regimens. The analysis will ascertain the number of patients exposed to RPV-containing regimens and EFV-containing regimens. The prescriptions will be summarized by patient demographics (age, sex, geography) and clinical characteristics (comorbidities and concomitant medications). In addition, the details of RPV and EFV-containing regimens use patterns will be described including duration of use, persistence of therapy, and usage of other HIV treatments.

This analysis will describe and summarize the utilization patterns of RPV-containing regimens and EFV-containing regimens with respect to viral load, CD4 counts, pretreatment RPV-containing regimens resistance testing, adverse events, HIV treatment status (naïve/experienced), prior HIV treatment regimens, concomitant medications, comorbidities, and route of infection. The analysis will ascertain the number of patients initiating RPV-containing regimens and the proportion of patients treated in accordance with RPV products' SmPC. Proportions will be estimated separately for each recommendation of patient treatment. The denominator for each proportion will consist of the number of all patients initiating RPV-containing regimens included in the study. Proportions will be estimated separately using the following numerators:

- The number of patients naïve to HIV treatment regimens
- The number of patients with documented pre-treatment screening for ARV RAMs

• The number of patients initiating RPV-containing regimens with a baseline viral load ≤ 100,000 HIV-1 ribonucleic acid (RNA) copies/mL

Proper prescribing will be summarized by patient demographics and potential confounders.

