3.1.1. Inclusion Criteria

Patients who initiate therapy with RPV or EFV-containing regimens during the study period will be identified. Initiation of therapy is defined as first prescription for RPV or EFV-containing regimens documented in the HIV cohort. Patients will be included in the study if they meet all of the following criteria:

- Have documented enrollment in the HIV cohort database prior to the start of RPV or EFV-treatment regimens;
- Have received at least one prescription for RPV-containing regimens or EFVcontaining regimens

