3.1.2. Exclusion Criteria

No specific exclusion criteria will be applied in this study.

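### The primary viral-load proportion is fixed over all RPV initiators with no rule for an unrecorded baseline value, so applied as written it would be understated wherever values are missing, and section 4.4 does not settle the handling.

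*Protocol*

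**What the plan says.** Section 4.5.2 of the protocol estimates one proportion per SmPC recommendation, all on a common base: "The denominator for each proportion will consist of the number of all patients initiating RPV-containing regimens included in the study". The synopsis and section 1.3.1 set the same denominator.

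Two of the three numerators matter here. The viral-load numerator is "The number of patients initiating RPV-containing regimens with a baseline viral load ≤ 100,000" copies/mL. The resistance-screening numerator is "The number of patients with documented pre-treatment screening for ARV RAMs".

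Entry under 3.1.1 rests on two conditions: "Have documented enrollment in the HIV cohort database prior to the start of RPV" or EFV treatment, and "Have received at least one prescription for RPV-containing regimens" or the EFV equivalent. Neither asks for a baseline viral load. Section 3.1.2 adds: "No specific exclusion criteria will be applied in this study".

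On missing data, section 4.4 plans to compare patients with and without complete data, and then says: "Strategies for managing missing data may include limiting the analysis to patients with complete data or missing data imputation". It ties neither strategy to any particular endpoint.

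**The concern.** A patient without a recorded baseline viral load is in the denominator and cannot enter the numerator. Under the stated rule that patient is indistinguishable from one who started above 100,000. For the screening item this treatment is sound, because the item counts documentation and an absent record is itself the finding. For viral load it is not: an absent record does not show on which side of the limit the patient lay. One denominator rule is being applied to two different kinds of item.

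The figure is one of three that answer the primary question of whether RPV is used in accordance with the SmPC. A shortfall in records could be read as a shortfall in prescribing. Section 4.5.2 also summarises proper prescribing by patient characteristics, and the study may pool several national cohorts. Differences in completeness between cohorts could therefore look like differences in prescribing.

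**Working it through.** **Inputs.** From 4.1.1: n = 600 RPV patients, planning proportion 95%, stated error ±0.02. From 4.5.2: all-initiator denominator and the viral-load numerator. The share with no recorded baseline viral load, m, is not given in the protocol; 0% to 20% is assumed here to show the range.

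**Reproducing the plan's own figure.** Half-width = 1.96 × √(p(1 − p)/n). At p = 0.95 and n = 600 this is 1.96 × √(0.95 × 0.05/600) = 0.0174, which rounds to the stated 0.02. All twelve cells of the table in 4.1.1 reproduce to two decimals.

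**Effect of the stated rule.** Let p be the true share at or below 100,000 and let missingness be unrelated to viral load.

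- Reported proportion = p(1 − m)
- Shortfall = p × m
- Bounds for the share among all initiators: p(1 − m) if all missing patients are above the limit, p(1 − m) + m if all are at or below it

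With p = 0.95:

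| m (assumed) | Patients missing of 600 | Reported as written | Shortfall | Bounds | Half-width among recorded values |
|---|---|---|---|---|---|
| 0% | 0 | 0.950 | 0 | 0.950 to 0.950 | 0.0174 (n = 600) |
| 1% | 6 | 0.9405 | 0.0095 | 0.9405 to 0.9505 | 0.0175 (n = 594) |
| 2% | 12 | 0.931 | 0.019 | 0.931 to 0.951 | 0.0176 (n = 588) |
| 5% | 30 | 0.9025 | 0.0475 | 0.9025 to 0.9525 | 0.0179 (n = 570) |
| 10% | 60 | 0.855 | 0.095 | 0.855 to 0.955 | 0.0184 (n = 540) |
| 20% | 120 | 0.760 | 0.190 | 0.760 to 0.960 | 0.0195 (n = 480) |

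**When the shortfall exceeds the planned precision.** Setting p × m equal to the half-width gives m = half-width/p. At p = 0.95: 0.0174/0.95 = 1.8%, about 11 of 600. The same step gives 2.7% at p = 0.90, 4.0% at p = 0.80 and 5.2% at p = 0.70.

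**Direction.** If missingness is related to viral load, the shortfall is the fraction of all initiators who are both unrecorded and truly at or below the limit. That lies between 0 and m, so the figure as written can be too low or correct, never too high.

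**What 4.4 does to this.** Complete-case analysis would replace the denominator with patients who have a value, against the text in three places. Imputation would keep all initiators and fill the numerator, so it is compatible with 4.5.2, but it is only offered as a possibility. If neither is applied, the literal rule stands. One primary figure thus has three possible constructions, and they give different answers whenever m is above zero.

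**The case against.** The strongest reply is that 4.5.2 should not be read apart from 4.4. Section 4.4 applies to the whole study, and imputation under it would remove the problem without touching the denominator. Which strategy goes with which variable is commonly left to a statistical analysis plan, and that plan is not at hand. This stands in part: the choice of method can wait. The denominator, however, is not left open. The protocol fixes it in the primary objective itself, and one of the two strategies it names contradicts that.

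A second reply is that missing values may be rare. Section 2.2 describes viral load among systematically collected variables and says the data needed for the regulator's request are available in the cohorts, apart from robust food-intake and adherence measures. Cohorts are also to be chosen after a feasibility assessment of the necessary variables. This bears on likelihood and stands. It does not guarantee a baseline value for each patient. Section 5 concedes in general terms that essential data may be lacking, without naming viral load.

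Third, counting only documented conformity over all initiators is a defensible conservative choice, and viral load at treatment start is described separately as a secondary objective, so the share above 100,000 need not be inferred by subtraction. This also stands, and it is why the all-initiator figure should be kept as a bound.

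A reader might go further and infer that the protocol scores every patient without a value as treated outside the SmPC, or that appropriate use as a whole will be understated. The documents do not support either. No section says such patients are so classified or that the complement will be reported as off-label use. The three proportions are reported separately, and the screening item is not affected in this way.

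**Conclusion.** The point holds as a conflict between a fixed rule and an optional one. Applied literally, the all-initiator denominator can only lower the viral-load proportion or leave it unchanged. The size depends on a missing rate that the protocol does not give: nothing at m = 0, and at p = 0.95 more than the planned half-width once m is above about 1.8%. The larger figures in the table, such as 4.75 points at 5% missing, are illustrations under assumed rates with missingness unrelated to viral load. They are not predictions.

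The conclusion is limited to this one primary proportion. It does not show that the result will be biased, because values may be nearly complete or imputation may be used. It shows that the protocol has not settled how the figure is built, and that little missingness is needed for this to matter more than sampling error.

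**What to change.** In the synopsis, 1.3.1 and 4.5.2:

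- Classify baseline viral load as at or below 100,000, above 100,000, or not recorded.
- Report the not-recorded share overall and by cohort.
- Report the proportion at or below 100,000 among patients with a recorded value.
- Report it also over all initiators, with unrecorded patients counted as all out (the current figure, now labelled a lower bound) and as all in (the upper bound).

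In 4.4, state that this handling applies to the viral-load proportion, so that the section no longer conflicts with the stated denominator.

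The recorded-value proportion is unbiased only if missingness is unrelated to viral load, so it should be shown with the bounds and not in place of them. The cost is a few sentences, some extra table rows, and a slightly wider interval for the recorded-value proportion: at p = 0.95 the half-width goes from 0.0174 to 0.0195 with 20% missing, which still rounds to the stated 0.02.

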1. INTRODUCTION

1.1. Background

Rilpivirine (RPV) is an NNRTI for the treatment of HIV-1 infection in antiretroviral treatment-naïve adult patients with a baseline viral load \leq 100,000 HIV-1 RNA copies/mL. RPV will be available as two formulations on the European market: a single agent, marketed by Janssen-Cilag International NV, and a fixed-dose combination containing FTC/RPV/TDF, marketed by Gilead Sciences International Ltd. The CHMP has requested further assessment of the development of resistance and whether the product is used in accordance with the Summary of Product Characteristics (SmPC). The development of resistance and the utilization of RPV according to the SmPC will be assessed through a drug utilization study (DUS) conducted in HIV observational cohorts within Europe. Additionally, the DUS will provide context to the observed rates of virologic failure and development of resistance by describing the treatment outcomes of patients treated with efavirenz (EFV). The relative risk of virologic failure and resistantassociated mutations (RAMs) after initiating RPV-containing regimens will be estimated separately by comparing the incidence rates of virologic failure and RAMs among RPVtreated patients to the incidence of virologic failure and RAMs among EFV-treated patients.

Several factors have been shown to be associated with virological response to antiretrovirals (ARV) for the treatment of HIV-1, including the degree of immunodeficiency and level of plasma HIV RNA when therapy is initiated, antiretroviral experience, drug resistance, and type of and adherence to the therapeutic regimen (Hull, 2009).

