1.3. STUDY OBJECTIVES

1.3.1. Primary Objectives:

The primary objectives were specifically chosen to meet the CHMP request to assess appropriate use of RPV-containing products. For all primary objectives, frequency and rates will be reported separately for the RPV and EFV-treated groups.

- To describe the proportion of patients treated with RPV-containing products in accordance with the SmPC. The proportion of patients treated with RPV in accordance with the SmPC will be described by estimating a proportion separately for each recommendation of patient treatment. The denominator for each proportion will consist of the number of all patients initiating RPV-containing regimens included in the study. Proportions will be estimated separately using the following numerators:
 - The number of patients naïve to HIV treatment regimens
 - The number of patients with documented pre-treatment screening for ARV RAMs
 - \circ The number of patients initiating RPV-containing regimens with a baseline viral load \leq 100,000 HIV-1 ribonucleic acid (RNA) copies/mL
- To describe treatment emergent RAMs in patients treated with RPV or EFVcontaining regimens
- To describe virologic failure in patients treated with RPV or EFV-containing regimens

The primary objective of the nested case-control analysis is to quantify separately the risk of virologic failure associated with ARV treatment adherence and pill intake with food.

1.3.2. Secondary Objectives:

The secondary objectives were specifically chosen to assist in meeting the CHMP request to assess appropriate treatment of patients with RPV-containing products in accordance with the SmPC or to provide context to events observed within the RPV-treatment group. For all secondary objectives, frequency and rates will be reported separately for the RPV and EFV-treated groups, as well as for RPV relative to EFV.

• To describe the demographic characteristics, comorbidities, and medical condition of patients initiating RPV or EFV treatment

- To describe antiretroviral (ARV) treatment status (naïve/experienced) of patients prior to initiating RPV or EFV treatment
- To describe prior use of ARV treatment, if any, of patients initiating RPV or EFV-containing regimens
- To describe the frequency of pre-treatment RAMs for RPV and EFV among patients subsequently initiating RPV or EFV treatment respectively
- To describe viral load at start of RPV or EFV treatment
- To describe viral load over the course of RPV or EFV treatment

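### No joint proportion is defined for the treatment-naïve and ≤100,000 copies/mL indication, and the viral-load proportion mixes naïve with experienced patients

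*Protocol*

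**What the plan says.** The first primary objective in section 1.3.1 is "To describe the proportion of patients treated with RPV-containing products in accordance with the SmPC". Section 4.5.2 puts it into practice: "Proportions will be estimated separately for each recommendation of patient treatment". It then fixes three numerators:

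- "The number of patients naïve to HIV treatment regimens"
- those whose records show resistance testing before RPV was started
- "The number of patients initiating RPV-containing regimens with a baseline viral load" of at most 100,000 copies/mL

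It also fixes one denominator for all three: "The denominator for each proportion will consist of the number of all patients initiating RPV-containing regimens included in the study". The Synopsis and section 1.3.1 give the same construction.

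Section 1.1 gives the indication as "treatment of HIV-1 infection in antiretroviral treatment-naïve adult patients with a baseline viral load" of at most 100,000 copies/mL. That is one condition in two parts, and both parts must hold in the same patient.

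The population is not limited to naïve patients. Section 3.1.2 applies no exclusions. Section 4.2.2 has a separate failure rule for patients undetectable at baseline. Section 4.5.3 stratifies virologic failure by naïve/experienced status.

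**The concern.** The study was requested to show whether RPV is used as labelled. The label restriction quoted in the protocol is a conjunction, but each part is counted separately over all initiators.

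An experienced patient who switches to RPV while suppressed is outside the indication as the protocol states it. That patient is missing from the naïve numerator but present in the viral-load numerator. The more such patients there are, the better the viral-load figure looks.

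A reader given only the separate proportions cannot tell how many patients were treated within the indication. That number is the natural summary of the first primary objective.

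**Working it through.** **1. The protocol's own precision figures.** Section 4.1.1 gives a 95% CI half-width of 0.02 at a proportion of 95% with 600 patients. The formula is 1.96 × √(p(1−p)/n).

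- p = 0.95, n = 600: 0.0174, which rounds to 0.02.
- p = 0.70, n = 600: 0.0367, which rounds to 0.04.
- All 12 table entries (70% to 95%, n = 400 and 600) reproduce to two decimals.
- The worst case, p = 0.50 with n = 600, gives 0.040. A joint proportion of any size therefore stays within the protocol's 5% target.

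**2. What the separate proportions say about the joint share.** Let p1 be the naïve proportion and p2 the viral-load proportion, both over all RPV initiators. With nothing else known, the share meeting both lies between max(0, p1 + p2 − 1) and min(p1, p2).

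- p1 = p2 = 0.95: from 0.95 + 0.95 − 1 = 0.90 to 0.95.
- p1 = 0.80, p2 = 0.85: from 0.80 + 0.85 − 1 = 0.65 to 0.80.

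These limits are arithmetic. They describe what the figures leave undetermined, which is distinct from sampling error. More patients would not narrow them.

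**3. Effect of experienced patients on the viral-load proportion.** Let s be the naïve share, v the share of naïve patients at ≤100,000 and e the same share among experienced patients. The documents give none of these, so all are assumptions.

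- Reported viral-load proportion: s·v + (1−s)·e
- Share within the indication: s·v
- Difference: (1−s)·e

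With v = 0.70 and e = 0.98:

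| Naïve share s | Reported viral-load proportion | Naïve and ≤100,000 |
|---|---|---|
| 0.9 | 0.630 + 0.098 = 72.8% | 63% |
| 0.7 | 0.490 + 0.294 = 78.4% | 49% |
| 0.5 | 0.350 + 0.490 = 84.0% | 35% |
| 0.3 | 0.210 + 0.686 = 89.6% | 21% |

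Varying v from 0.6 to 0.8 with e = 0.98:

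- s = 0.9: reported 63.8% to 81.8%, joint 54% to 72%.
- s = 0.3: reported 86.6% to 92.6%, joint 18% to 24%.

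Whenever e exceeds v, the two columns move in opposite directions as the naïve share falls.

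**4. Is the cross-tabulation promised elsewhere?** Section 4.5.2 describes utilization with respect to viral load and to treatment status, but lists them as separate items. The explicit naïve/experienced stratification in section 4.5.3 covers virologic failure only. Neither commits to viral load by treatment status.

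**The case against.** The best defence is that the separate proportions are deliberate. Sections 1.3.1 and 4.5.2 say that the objective will be described recommendation by recommendation, in a study that section 4.3.1 calls descriptive. That stands. A reader might infer that the primary objective is never computed, but the protocol defines it by the three proportions and plans all three. The gap is the absence of a joint figure beside them.

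Second, the naïve proportion is reported openly and caps the joint share. In the last row of the table the plan would show 30% naïve, so nobody could take 89.6% as the share within the indication. That also stands, and it limits the harm. It does not supply the joint figure, and the viral-load proportion on its own remains hard to interpret.

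Third, section 4.1.1 says that 600 patients are included "to assess the proportion of appropriate use of RPV formulations", in the singular. A reader might infer that the sizing applies to a quantity the plan does not estimate. The documents do not support this as a fault: the Synopsis states the error rate for the proportions estimated, in the plural, the table applies to each of them, and 600 patients also suffice for a joint proportion.

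Fourth, a reader might infer from the fixed denominator that a patient without a baseline viral load is counted as not in accordance. Section 4.4 leaves open complete-case analysis or imputation, so this is not established.

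Finally, a statistical analysis plan could add the cross-tabulation. It could, but the protocol itself fixes the numerators and the denominator for a primary objective, so the addition belongs there.

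**Conclusion.** The point holds as a gap in how the first primary objective is summarised. The protocol states a two-part indication, defines no numerator for patients who meet both parts, and reports viral load over a mixed naïve and experienced population.

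The indeterminacy is 5 percentage points when both proportions are 95% and 15 points when they are 80% and 85%. Those widths need no assumption beyond the proportions chosen. The divergence in the table depends on assumed values of s, v and e. Its direction requires only that experienced initiators are at ≤100,000 more often than naïve ones.

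Documented resistance screening is a separate recommendation in section 4.5.2 and is not part of the indication as section 1.1 words it. A three-condition figure should therefore not be read as the share within the indication.

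**What to change.** In sections 1.3.1 and 4.5.2 (and the Synopsis):

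- Keep the three proportions as they are.
- Add, with 95% CI, the proportion of all RPV initiators who are both treatment-naïve and at ≤100,000 copies/mL at baseline.
- Beside it, give the proportion who also have documented pre-treatment resistance screening.
- Report the viral-load proportion by naïve/experienced status.

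The cost is one more cross-tabulation of data already collected, and a headline figure that can only be equal to or less favourable than the separate proportions it combines. No extra patients are needed: at n = 600 the half-width is at most 0.040.
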